### **8.4 Secondary Endpoints**

#### **8.4.1 Scale for Oral Pain, xerostomia**

Oral discomfort and xerostomia will be measured by 0-10 scale (Appendix A). We will use this scale to evaluate changes in oral pain and xerostomia over the course of treatment at end of study.

#### **8.4.2 GVHD Severity Scale**

Few objective scales assessing severity of oral chronic GVHD in a standardized way have been published. One of the recently developed systems [48] (Appendix B) has been shown to have good reproducibility and assesses the oral cavity by site (e.g. labial mucosa, dorsal tongue, gingiva) and lesion type (lichenoid, erythematous, ulcerative). Scoring will be performed by investigators trained in assessment of oral cavity lesions. The results will be correlated with scores from the symptom-oriented instruments and the global scale. We will also use a simplified 6 point scale developed for oral lichen planus – a condition that closely resembles oral GVHD [49] (Appendix C). For the purposes of this study we will consider a grade of 3 or higher a clinically significant oral chronic GVHD.

#### **8.4.3 Patient-assessed Global Scale (perception of changes in oral condition)**

We will also assess subjects' perceptions of the changes in the oral condition on a 5 item scale (Much worse, A little worse, same, a little better, much better). The data will be correlated with the results from the numerical scoring system to assess internal validity.

#### **8.4.4 Oral Health Impact Profile-14**

Oral Health Impact Profile-14 (OHIP-14, Appendix D) is a 14 item questionnaire developed to assess the state of oral health as perceived by a patient [50, 51]. Increased use of patient centered outcome measures has been advocated in the recent years. Patient centered outcome measures complement objective measures

to provide a more complete picture of the impact of disease and treatment. OHIP-14 has been used in oral disease studies including oral lichen planus (a dermatological condition with manifestation similar to chronic oral GVHD). It has been shown to have high validity and reliability, and to be sensitive to treatment effects. This scale has not been well studied in children; therefore it will be limited to adults.

#### 8.4.5 Dexamethasone levels

Systemic absorption of dexamethasone oral solution will be evaluated by measuring plasma dexamethasone levels at the 3 month follow-up appointment. Dexamethasone levels will be blinded to the investigators until the end of the study.

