## 1.2 Secondary Objectives

- 1.2.1 To assess the incidence, risk factors and clinical characteristics of oral chronic GVHD.
- 1.2.2 To evaluate the impact of oral chronic GVHD on quality of life.
- 1.2.3 To evaluate the degree of systemic absorption of topical dexamethasone and its effect on adrenal cortical function.
- 1.2.4 To evaluate changes in salivary and plasma proteome associated with oral chronic GVHD.
- 1.2.5 To evaluate tissue kinetics and gene expression patterns of immune cells associated with the development of chronic oral GVHD and prophylaxis with topical dexamethasone.
- 1.2.6 To assess the predictive value of subclinical tissue changes on development of chronic oral and systemic GVHD and prognostic significance of these changes in terms of graft versus tumor effect.

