## **2.5 Scientific and Clinical Justification**

Prevention of oral GVHD by topical agents is an attractive strategy because it would potentially avoid the adverse effects associated with systemic immunosuppression. Most importantly, using immunosuppressive and tolerizing agents locally would concentrate the effects in the area where they are beneficial, as GVHD occurs in response to recognition of peripheral antigens by activated donor T-cells. Conversely, use of systemic agents for the same purpose would interfere not only with the undesirable GVH response, but also with immune responses directed against the malignancy (i.e. the graft vs. tumor effect), which is the principal mechanism through which reduced intensity transplants achieve sustained disease remission.

There are no studies of dexamethasone absorption when used topically in the oral cavity and expectorated. The systemic effects of topically administered dexamethasone solution have not been investigated. Since this is a commonly used agent for the treatment of oral inflammatory conditions including GVHD, knowledge of the degree of systemic action would be valuable. If the absorption is significant, some degree of adrenal suppression is likely. This may have implications in many situations when systemic effects of steroids are undesirable.

We therefore propose a trial of topical dexamethasone solution for prevention of chronic oral GVHD in stem cell transplant recipients ages 12 and older. Additionally, this study will provide valuable insights into the cellular and molecular alterations associated with the development of chronic GVHD and treatment with topical corticosteroids. This will lead to better understanding of the pathogenesis of chronic GVHD and potentially development of new therapeutic interventions.

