### **5.2.2 *Post transplant medications***

There will be no prohibited interventions for this study except topical agents for oral GVHD. All interventions and medications dictated by the subject's primary transplant protocol and clinical necessity will be permitted. Subjects will be queried at interim assessments regarding topical and systemic analgesic use. Factors that can potentially confound the results (such as systemic steroids and other immunosuppressants) will be tracked and taken into consideration at the time of the final statistical analysis.

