### **6.3 End of Treatment Monitoring and Assessments (3 months)**

Subjects will be evaluated at the NIH at 3 months (+/- 7 days) after starting study medication with the following assessments:

- Interim assessment
- Blood pressure
- Concomitant meds (immunosuppressive, antimicrobial and analgesics)
- The 0-10 Scale for Oral Pain (see Appendix A)
- The 0-10 Scale for Oral Xerostomia (see Appendix A)
- Patient-assessed Global Scale (perception of changes in oral condition-Appendix A)
- GVHD Severity Scale (see Appendix B)
- Lichen Planus (oral GVHD) Severity Scale (see Appendix C)
- Disease specific QOL- OHIP-14 scale (ages 18 and older only) (Appendix D)
- Complete blood count (CBC with diff) – done concurrently with post transplant monitoring
- Serum chemistry (Acute Care (Na, K, Cl, CO2, Creatinine, Glucose, and Urea Nitrogen), Mineral (Phosphorus, Magnesium, Albumin, and Calcium), Hepatic (Alk Phosphatase, ALT, AST, Total Bilirubin, and Direct Bilirubin), and Other (Total Protein, CK, Uric Acid, and LD) panel) – done concurrently with post transplant monitoring
- Serum cortisol level (results blinded to investigators)
- ACTH stimulation test (Optional)
- Serum dexamethasone level (results blinded to the investigators)
- Buccal mucosal less than approximately 6mm punch biopsy ages 18 and older only (optional)
- Oral photographs (Optional)
- Oral lesion documentation
- Research blood sample collection
- Saliva sample collection
- Growth chart (length for age, weight for age percentiles and body mass index for age percentiles, pre-pubertal children) (if hand x-ray is available on parent transplant protocol, the results will be reviewed)

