## **6.6 Compliance**

Subject adherence to the trial interventions will be estimated by measuring the dexamethasone levels at time of analysis (the end of study assessment). Subject adherence to the trial interventions will be estimated by self-reporting compliance and the refill of study medication.

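### Systemic absorption rests on one dexamethasone level with no fixed or recorded time since the last rinse, so a low value cannot be read as low absorption

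*Combined protocol and SAP*

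**What the plan says.** Section 1.2 lists as objective 1.2.3: "To evaluate the degree of systemic absorption of topical dexamethasone and its effect on adrenal cortical function". Section 2.5 says why this is worth knowing: "There are no studies of dexamethasone absorption when used topically in the oral cavity and expectorated".

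The method is one sentence in Section 8.4.5, under which absorption is assessed by "measuring plasma dexamethasone levels at the 3 month follow-up appointment". The visit is defined in Section 6.3: "Subjects will be evaluated at the NIH at 3 months (+/- 7 days) after starting study medication". A serum dexamethasone level is on that visit's list and on no other. Section 8.5 sets the intervention at 3 months, with three rinses a day (Section 5.1).

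Section 6.6 gives the level a second use: "Subject adherence to the trial interventions will be estimated by measuring the dexamethasone levels at time of analysis". It places that level at the end of study assessment and then also names self-report and medication refills. The assessments in Section 6.5 include no dexamethasone level. The Précis says levels will be measured at the end of the 3 months or at onset of clinically significant GVHD.

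On concomitant drugs, Section 5.2.2 states: "There will be no prohibited interventions for this study except topical agents for oral GVHD". It goes on to say that systemic steroids will be tracked and considered in the final analysis.

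**The concern.** A blood level reflects how much drug was absorbed and how long ago. With one sample and an unknown time since the last rinse, the two cannot be separated. Missed rinses add a third explanation for a low value. Because no earlier absorption data exist, there is no reference range against which to read an untimed level.

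Late draws and missed rinses both push the value down. At stake is a reassuring statement about absorption that the data could not support, for a regimen that Section 5.1.1 equates with about 20 mg prednisone a day if swallowed. If the time of the last rinse is not collected at the visit, the analyst has no reliable way to reconstruct it. The protocol does fix sampling times where it needs them: the cosyntropin test in Section 8.4.6 has a morning clock window and draws at 30 and 60 minutes.

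**Working it through.** **The plan's own exposure figure.** Each rinse contains 1 mg and 0.75 mg dexamethasone equals about 5 mg prednisone (Section 11.1); there are three rinses a day (Section 5.1). So 3 x 1 mg / 0.75 mg x 5 mg = 20 mg prednisone a day, which agrees with Section 5.1.1. The figure is not in dispute.

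**What fixes the sampling time.**
- Section 6.3: the visit is 3 months +/- 7 days from first dose. No hour of day, no interval from a rinse.
- Section 8.4.5: the month-3 appointment. No interval from a rinse.
- Section 8.5: treatment lasts 3 months. No section says whether rinsing ends on a calendar date or continues to the visit.
- Section 6.6: the adherence level is at the end of study assessment, where Section 6.5 lists none. The month-3 sample is thus the only scheduled one that could serve.
- Précis: the level may instead be taken at GVHD onset. Subjects reaching the endpoint go to the end of study assessments (Section 5.3), which again list none.
- Section 8.4.6, item 1: completion of the interventional phase is described as 3 months after the last dose, which does not fit Sections 6.3 and 8.5.

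**How much timing could matter.** The documents give no half-life, so I assume 3 to 24 h for illustration. With first-order decay, fraction left = 0.5^(t / half-life), where t is the time since the level just after absorption of the last rinse.

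| Assumed half-life | 1 h | 12 h | Ratio, 1 h to 12 h | 24 h | 48 h | 7 days |
|---|---|---|---|---|---|---|
| 3 h | 79% | 6.3% | 12.7 | 0.4% | 0.0015% | <0.001% |
| 6 h | 89% | 25% | 3.6 | 6.3% | 0.4% | <0.001% |
| 12 h | 94% | 50% | 1.9 | 25% | 6.3% | 0.006% |
| 24 h | 97% | 71% | 1.4 | 50% | 25% | 0.8% |

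The ratio is 2^(11 / half-life); for 3 h, 2^(11/3) = 12.7.

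The 12 h column stands for an overnight gap. That is also an assumption, though a plausible one: Section 8.4.6 calls for morning cortisol and Section 11.1 has rinses after meals.

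**Same value, two explanations.** A five-fold lower level could come from five-fold lower absorption or from a draw later by half-life x log2(5): about 7, 14, 28 or 56 h for half-lives of 3, 6, 12 and 24 h. The first two are delays of a single day or night. The last two would need a subject who had missed rinses or stopped them.

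**The case against.** The strongest reply is that more is inferred from silence than the documents say. Much of it stands.

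- **Draws after treatment.** A reader might infer that levels will be drawn up to a week after the last rinse. No section says rinsing stops before the visit. Section 6.3 is titled as the end-of-treatment visit and half its window precedes 3 months, so rinsing up to the visit is a natural reading. The 7-day column is therefore conditional. The missing interval since the last rinse remains under either reading.
- **Adherence.** A reader might infer that the level is the only adherence measure. It is not: self-report and refills are listed and would help to flag missed rinses. They do not give the time of the last rinse.
- **Systemic steroids.** A reader might infer that systemic dexamethasone is ignored outside the adrenal analysis. Section 5.2.2 tracks systemic steroids, Section 8.5 plans stratified analyses for systemic immunosuppression, and the month-3 level is not restricted by arm, so placebo levels show background. High values are thus a lesser problem. They also push upward, so an overall bias toward finding no absorption cannot be claimed.
- **Size.** A reader who assumes a 3 to 6 h half-life gets a 3.6- to 13-fold swing. At 12 and 24 h it is 1.9- and 1.4-fold. Carry-over from earlier rinses is also ignored, although under first-order decay that changes the starting level and not the ratio between two times after the same last rinse.
- **Safety.** Adrenal effect is assessed separately through cortisol, with ACTH testing optional or prompted by symptoms. That covers the other half of objective 1.2.3 but does not measure absorption.

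The case report form is not in the documents and may already hold a rinse-time field. The protocol does not require one.

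**Conclusion.** The concern holds for low values. As written, the absorption half of objective 1.2.3 depends on one untimed level per subject, and a low level cannot distinguish low absorption from a late draw or missed rinses. A clearly detectable level in a subject not taking systemic dexamethasone would still show that absorption occurred. A higher mean than on placebo would point the same way; a similar mean would remain ambiguous.

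Under the assumed 3 to 24 h half-life, the within-day effect runs from about 13-fold down to 1.4-fold between 1 h and 12 h, so it may be large or modest. If rinsing does stop at 3 months, a level drawn 7 days later is under 1% of its starting value whatever was absorbed; at 48 h it could be anywhere from almost nothing to 25%.

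The documents do not support saying that off-drug draws will occur, that adherence rests on this level alone, or that systemic steroids are unaddressed. The point concerns a secondary objective and does not touch the primary endpoint or the sample size. It merits a change because the repair is cheap and must be made before the samples are taken.

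**What to change.** **Sections 6.3 and 8.4.5**
- Record the date and clock time of the last rinse and of the blood draw, and whether the subject is on study drug at the draw.
- Define a sampling window relative to a scheduled rinse while the subject is on study drug. Levels inside it form the main absorption summary, by arm, with placebo as background.
- Summarise levels drawn off study drug, or during systemic dexamethasone, separately.

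**Section 6.6**
- Judge adherence from the self-report and refill data already listed, not from the level used for absorption.

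**Reconcile**
- The Précis and Sections 6.3, 6.5, 6.6, 8.4.5, 8.4.6 and 8.5 should agree on when the level is drawn, whether one is taken at GVHD onset, and when treatment ends relative to the month-3 visit. This is a request for consistency; treatment duration is for the sponsor and investigators to state.

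**Cost.** Amendment wording and two time fields on the form, with the same visit and the same blood sample. The visit has to be scheduled around a rinse, and its order relative to saliva collection and the optional biopsy must be set, given the 30-minute restriction after each rinse.

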#### 8.4.6 Assessment of adrenocortical function (cortisol levels)

Subjects will be evaluated for possible hypothalamic-pituitary axis (HPA) axis suppression with the following measures:

1. Morning cortisol levels will be determined at baseline, monthly follow-ups (done at NIH), and at completion of the interventional phase (3 months after the last dose of study medication). The results will be blinded to the investigators until the end of the study. At the end of the study, in subjects with morning cortisol levels between 19 mcg/dL and 3 mcg/dL no further adrenal function testing will be performed.
2. In subjects with the symptoms of suspected adrenal insufficiency, a Short Cosynthropicin Test (SCT) will be performed to determine if the subject has HPA axis suppression. In brief: venous blood will be collected before administration of 250 mcg of cosyntropicin (synthetic ACTH) around 8 AM to 12 noon, and at 30 and 60 minutes after. The expected rise in cortisol levels is to at least 18 mcg/dL (24). In cases of minimally abnormal SCT (stimulated cortisol values of 13-17 mcg/dL), the test will be repeated the next day, as it has been demonstrated that the result is often normal with a repeat test. This test has been shown to be sensitive and specific for evaluation of subclinical adrenal suppression [52, 53]. In the unlikely event of significant adrenal suppression as assessed by repeat ACTH stimulation test, Clinical Center Endocrinology Service will be consulted. Pharmacy will be requested to unblind therapy to the endocrinologist so that appropriate therapy can be initiated and the endocrinologist can appropriately attribute the relationship of the event to study drug administration.
3. The confounding effect of systemic corticosteroids will be taken into account at the time of analysis. We expect to have a subgroup of subjects who will not receive systemic steroids. This subgroup will be used to evaluate the effects of topical dexamethasone on adrenal secretion.

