## PRÉCIS

Prevention of oral chronic graft versus host disease (GVHD) by topical agents is an attractive strategy because it would potentially avoid the adverse effects associated with systemic immunosuppression. Topically administered dexamethasone solution is a commonly used agent for the prophylaxis of oral inflammatory conditions including GVHD. However, the efficacy and systemic effects of topically administered dexamethasone solution are unknown. We therefore propose this trial designed to evaluate the efficacy and safety of topical dexamethasone solution for prevention of oral chronic GVHD in stem cell transplant recipients.

This pilot phase II study will follow a randomized, double-blind, placebo controlled, parallel group design. Consenting subjects who have undergone hematopoietic stem cell transplantation at the NIH Clinical Center and the surrounding transplant clinics will be randomized 50/50 to receive dexamethasone 0.01% solution or placebo as an oral rinse for 3 months starting 90-100 days post-transplant. Subjects will be evaluated monthly after the start of intervention. Diagnostic and research evaluations will include a complete oral examination, oral mucosal biopsy prior to the beginning of the intervention (day -7) and at the time of development of oral chronic GVHD or at the completion of intervention in the absence of clinical GVHD. We will measure serum dexamethasone levels and perform short cosyntropin (ACTH stimulation) test at the end of the 3 months of intervention or onset of clinically significant GVHD.

The primary objective of the study is to evaluate the safety and efficacy of topical dexamethasone 0.01% solution used as an oral rinse for prevention of oral chronic GVHD. Our primary endpoint will be the proportion of subjects that develop clinically significant (severity score 3 or higher) oral chronic GVHD after three months.

Secondary objectives will include the impact of oral chronic GVHD on the quality of life, characterization of the changes in tissue and salivary biomarkers associated with development of oral graft versus host disease, and measures of the effects of topical dexamethasone on hypothalamo-pituitary-adrenal axis. Secondary outcomes will include oral cavity specific quality of life as measured by OHIP-14 questionnaire, oral discomfort levels, improvement in general quality of life scores, and severity of oral chronic GVHD as measured by the site-specific GVHD scoring system.

---

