### **10.3 Risks and Discomforts**

#### **10.3.1 Related to dexamethasone**

The side-effects of topical steroids are usually limited to Candida (yeast) infection. This is relatively uncommon in our subject population (<5%), easily treatable and does not require discontinuation of the prophylaxis.

Low levels of topical steroids are absorbed through the oral mucosa, but the exact rate is not known. Possible risks associated with absorbed drug include:

- Adrenal suppression: While adrenal suppression is very rare with topically applied corticosteroids, it is physiologically possible. Cases of adrenal suppression following topically-applied steroid creams have been reported with long-term use on extensive body surface primarily in young children. In other reports, it was difficult to determine if there was true adrenal suppression. Symptoms of adrenal suppression are non-specific and include fatigue, nausea and abdominal discomfort. Since these symptoms are extremely common in the general hospital population, routine monitoring in the context of this study is not indicated. In this study, blood pressure will be monitored at every visit, and adrenal function will be assessed at the end of prophylaxis. Given the very short duration of this study, we do not expect significant side effects.

In the unlikely event of significant adrenal suppression as assessed by repeat ACTH stimulation test, Clinical Center Endocrinology Service will be consulted (see section 8.4.6, Assessment of Adrenocortical Function [Cortisol] levels).

- Growth and bone health: Impairment of childhood growth with an approximate cortisone dose of 1.5 mg/kg/day was first described over 40 years ago; osteopenia in children receiving a prednisolone dose of less than 0.16 mg/kg/day has also been reported. Loss of bone and deterioration in short term growth are dependent on the type and dose of glucocorticoid and occur most prominently over the first six months of treatment.

We will monitor pre-pubertal pediatric subjects by use of growth chart (length for age, weight for age percentiles and body mass index for age percentiles) and bone age (hand x-ray) if the results are available on the parent transplant protocol.

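### The adrenal and dexamethasone measurements carry conflicting dates (8.4.6, 6.6), early-GVHD subjects have no listed draw, and the cortisol blinding is not reconciled with the 5.4.2 retest

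*Combined protocol and SAP*

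**What the plan says.** All references are to the combined protocol and SAP.

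**Cortisol.** Section 8.4.6 asks for a morning cortisol at baseline, at monthly follow-ups done at NIH, and "at completion of the interventional phase (3 months after the last dose of study medication". Section 6.3 lists a serum cortisol for subjects "evaluated at the NIH at 3 months (+/- 7 days) after starting study medication". Section 10.3.1 states that "adrenal function will be assessed at the end of prophylaxis".

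**Dexamethasone.** Section 6.6 estimates adherence by "measuring the dexamethasone levels at time of analysis (the end of study assessment", and also by "self-reporting compliance and the refill of study medication". Section 6.3 lists "Serum dexamethasone level (results blinded to the investigators" at the month-3 visit, and 8.4.5 evaluates absorption by "measuring plasma dexamethasone levels at the 3 month follow-up appointment". The Précis says "We will measure serum dexamethasone levels and perform short cosyntropin (ACTH stimulation) test at the end of the 3 months of intervention" and then gives onset of clinically significant GVHD as the alternative time. The 6.5 list for the end of study visit contains neither a cortisol nor a dexamethasone assay. It does contain a research blood sample.

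**Blinding and retest.** Section 6.3 blinds the cortisol result to the investigators, and 8.4.6 keeps it blinded until the end of the study without defining that point. Section 5.4.2 says that asymptomatic subjects with an abnormal ACTH or cortisol result at the end of the intervention may be observed and retested 1 month later. The ACTH stimulation test is optional in 6.3 and prompted by symptoms in 8.4.6. Its results are not stated to be blinded.

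**The concern.** Objective 1.2.3 is the systemic absorption of the rinse and its effect on adrenal function. Section 2.5 says that neither has been studied for this use. The sections defining these measurements should each give one date, and that date should match a visit at which the sample is drawn.

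A cortisol drawn 3 months after the last dose describes recovery, not suppression on treatment. A dexamethasone level drawn 6 months after the last dose says nothing about absorption or adherence. If site staff or the analyst followed the 8.4.6 parenthesis or the 6.6 wording for subjects who complete treatment, the values could not serve their purpose.

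Two gaps sit beside this. Subjects who reach the endpoint during treatment leave through the 6.5 visit. There the Précis expects a dexamethasone level and an ACTH test, and the list provides no adrenal or dexamethasone assay. Also, one trigger for the 5.4.2 retest is a result that the investigators are not meant to see, and no reader outside the blind and no release rule is named.

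**Working it through.** This is a check of dates and visit lists. The plan states no figure to reproduce.

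**Inputs** (month 0 = first dose): intervention of 3 months (8.5); end-of-treatment visit at 3 months ± 7 days (6.3); remote contacts at months 4 to 8 (6.4); final evaluation 6 months after the intervention (7.1, 8.5; the 6.5 body and 8.8.3 agree); retest 1 month after the intervention (5.4.2); drug start on day 90–100 after transplant (Précis).

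**Dates for subjects who complete treatment**

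| Item | Source | Month | Months off drug |
|---|---|---|---|
| Cortisol | 8.4.6 main clause, 6.3, 10.3.1 | 3 | 0 |
| Cortisol | 8.4.6 parenthesis | 3 + 3 = 6 | 3 |
| Dexamethasone | 6.3, 8.4.5, first branch of the Précis | 3 | 0 |
| Dexamethasone | 6.6, at the end of study visit | 3 + 6 = 9 | 6 |

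The zeros assume that dosing continues to the visit. If it stops at exactly 3 months, the 6.3 window allows a draw up to 7 days after the last dose.

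**Which month is the end of study?** The 6.5 heading gives 6 months after starting the drug, against month 9 elsewhere. Section 7.1 equates the visit with 12 months post-transplant, which allows a check, assuming 30.4 days per month:
- Month 9: (90 to 100) + 9 × 30.4 = day 364 to 374, or 12.0 to 12.3 months.
- Month 6: (90 to 100) + 6 × 30.4 = day 272 to 282, or 9.0 to 9.3 months.

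Month 9 fits, and the 6.5 heading is the outlier.

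**Is any later assay scheduled?** Section 6.4 lists no blood draw, and 6.5 lists neither assay. Month 3 is the only post-baseline visit whose list includes cortisol or dexamethasone.

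**Subjects with GVHD during treatment.** Sections 5.3, 8.5 and 8.8.2 send them to end of study assessments and then off study. Onset therefore coincides with the 6.5 visit, possibly while still on drug. For them the visit named in 6.6 agrees with the second branch of the Précis. The conflict is with the 6.5 list.

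**Blinding against the retest.** The retest is at month 3 + 1 = 4. Release of cortisol minus retest:
- End of the study means end of intervention: 3 − 4 = −1 month, no gap.
- It means the subject's last visit: 9 − 4 = +5 months (6 − 4 = +2 by the 6.5 heading).
- It means the end of the trial: later still, not computable.

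The documents do not settle which. Section 8.4.6 also ties the decision on further adrenal testing to morning cortisol at the end of the study, again without a definition. The only unblinding it describes is of treatment assignment to the endocrinologist, after an abnormal repeat ACTH test.

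**The case against.** The strongest reply is that the visit schedule is clear. Sections 6.3 and 8.4.5 put both draws at month 3, 10.3.1 agrees on adrenal function, and no visit list supports a later assay. The 8.4.6 parenthesis may be a slip for the first dose. Adherence also has self-report and refill behind it, and a dexamethasone level could inform on adherence to the rinse only in the active arm. This stands, and it limits the consequence: a site that follows 6.3 avoids the timing problem for completers. It does not remove two dates from one endpoint definition, or a visit reference that its own list contradicts.

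On blinding, much of the reply also stands. Section 5.4.2 is permissive, its firm advice to subjects depends on ACTH results, symptomatic subjects are covered by the cosyntropin test in 8.4.6, and 10.3.1 says routine monitoring for adrenal symptoms is not indicated. One reading of the end of the study leaves no gap. What remains concerns asymptomatic subjects without an ACTH result, whose number the documents do not give.

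A reader might infer that objective 1.2.3 cannot be answered, that adherence goes unmeasured, or that the retest cannot operate. The documents support none of these: the month-3 draw exists, other adherence measures are named, and the ACTH branch of 5.4.2 is open.

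**Conclusion.** The timing contradictions hold with high confidence. Section 8.4.6 dates one cortisol at both month 3 and month 6. Section 6.6 attaches the dexamethasone level to a visit that does not list it, at month 9 and 6 months off drug for completers. For subjects who develop GVHD during treatment, the Précis and the 6.5 list disagree on whether there is any measurement.

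The blinding point holds with moderate confidence and conditionally. Unless the end of the study means the end of the intervention, an isolated abnormal morning cortisol in an asymptomatic subject without an ACTH test would not be known to the investigators by about month 4. The delay would be 5 months at the subject's last visit (2 by the 6.5 heading), or longer.

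The month figures apply to completers only, because early leavers have their end of study visit at the event. Nothing here touches the primary endpoint. These are inconsistencies that should be corrected, not a flaw that invalidates the trial.

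**What to change.** 1. Correct the parenthesis in 8.4.6 and the visit reference in 6.6. For subjects completing treatment, the cortisol and dexamethasone values used for objective 1.2.3, and the dexamethasone level used for adherence, should be those of the existing 6.3 visit. State that the level informs on adherence in the active arm only.
2. Reconcile the GVHD-onset branch of the Précis with the 6.5 list, and state whether subjects who leave early with GVHD contribute a value. Limiting the analysis to the 6.3 visit without comment would drop them silently.
3. Define the end of the study in 8.4.6, and reconcile the cortisol blinding in 6.3 and 8.4.6 with 5.4.2. The clinical rule and the way to achieve this are the sponsor's choice.
4. Align minor wording at the same time: the monthly cortisol in 8.4.6, which is limited to follow-ups at NIH, against 6.2, which lists no cortisol; the 6.5 heading against its body; and the cosyntropin wording of the Précis, which is broader than 6.3 and 8.4.6.

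**Cost.** For completers this is wording only, with no new samples. Honouring the Précis for early-GVHD subjects would mean assays not now listed in 6.5. On blinding there is a trade-off: earlier access to cortisol could hint at treatment assignment, while later access can leave an isolated abnormal value unread at the retest month.
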